9.2.4 Secondary Endpoints

Secondary endpoints have been specified from several domains including a similar composite endpoint but defined on the basis of Day 21 mSOFA, individual components of the primary composite endpoint, time to resolution of organ dysfunction, critical care and hospital stay parameters (ICU and ICU-free days, ventilator days and –free days,

vasopressor days and -free days, hospital LOS), clinical local parameters (debridement history variables), and clinical systemic parameters (mSOFA over time, incidence and recovery from AKI). Analyses for these endpoint will generally be descriptive, with emphasis on characterizing clinical effect sizes. Nominal p-values will be presented. Categorical outcomes will be described using counts and percentages with nominal p-values determined through chi-square or exact methods. Critical care and hospital stay endpoints will be described using non-parametric approaches including using concordance statistics to characterize clinical effect size and Wilcoxon rank sum tests to determine nominal statistical significance. Methods appropriate for time-to-event endpoints including survival and life-table methods will be used for time-to-organ dysfunction resolution endpoints. Where appropriate, for continuous measures, statistical testing and estimation will be based on the results from a Mixed Model Repeated Measures (MMRM) analysis of covariance (ANCOVA) model. AKI endpoints will be assessed in several ways include incidence of Stage 2/3 AKI and among incident cases, resolution of AKI. A similar analysis will be performed based on any stage AKI. Treatment groups will be compared using counts and percentages with nominal p-values determined through chi-statistics.

9.2.5 Exploratory Analyses

Exploratory subgroup analysis will be performed. For these exploratory analyses, active dose versus placebo differences in NICCE will be evaluated in several subgroups defined by (i) severity of disease at baseline (3-4 vs >4), (ii) presence of non-Fournier's gangrene (iii) involvement of suspected superantigen-producing bacteria and (iv) type of bacteria (Gram-positive vs. Gram-negative). Other similar comparisons may be performed.

9.2.6 Assessment Of Poolability Among Sites

Site poolability will be evaluated using a random effects meta-analysis approach using the R package *metafor* to implement the analysis⁴². True effects are assumed to be normally distributed with mean μ and variance τ^2 . By imposing a specified distribution on the site-to-site variability, i.e. a normal distribution with mean μ and variance τ^2 , sensitivity to small sample sizes in individual sites is reduced and the parameters reflecting the magnitude of site-to-site variability are naturally derived. The quantitative measure of the magnitude of heterogeneity is I² ⁴³. I² is the fraction of τ^2 that is due to effect size heterogeneity, as opposed to sampling variance. Fractions 25% and less are considered small. If there is significant site to site variability, the impact on this variability will be evaluated using a random effects logistic regression to test the null hypothesis that the likelihood of achieving NICCE is the same for treated and placebo patients accounting for a random site effect. Poolability according to baseline demographic, disease severity status, and number of levels treated will be evaluated using descriptive stratified analyses.

9.2.7 Analysis Of Other Covariate Effects

Covariates will be assessed for potential confounding (due to lack of perfect randomization balance) or effect modification (subgroup efficacy heterogeneity) using multiple logistic regression. Covariates will include but are not limited to age, race, sex, site, and clinical severity scores at baseline. Other baseline variables in which randomization failed to

produce balance between groups will be examined in supporting analyses. This will be done through stratified analyses and multiple logistic regression. Covariate effects on estimates and interactions will be assessed to see if there is evidence of efficacy heterogeneity. Results from all subgroups analyses will be considered hypothesis-generating.

9.2.8 Multiplicity

There is a single primary hypothesis test utilizing a composite clinical success endpoint, NICCE and a conditional co-primary endpoint consisting of 3 of the 5 NICCE components. The use of a composite endpoint serves to address the multiplicity issue with regard to the key outcomes of mortality, local activity, and systemic activity⁴⁴. The co-primary endpoint will only be test if two-sided p≤0.01 in order to avoid the need for multiplicity adjustment and will be tested using a two-side α =0.05. The 5 components of NICCE will be individually evaluated in supporting analyses will no adjustment for multiplicity.

9.2.10 Analysis Of Event-time

Time to event endpoints will be assessed in descriptive analyses using survival and lifetable methods as appropriate. Results will be displayed in terms of morbidity/mortality or event rate ratios (i.e., incidence density ratios [IDR]) along with 95% confidence intervals. Analyses will include time to symptom resolution.

9.2.11 Handling Of Missing Data

9.2.11.1 Intent-to-Treat

The purpose of intent-to-Treat comparisons is to ensure that randomization is protected (i.e., all groups have comparable baseline characteristics and that any differences besides therapy are due to chance) and to preclude the possibility of bias due to selectively excluding subjects from therapy groups. This is intended to avoid systematic differences among the groups attributable to factors other than therapy assignment⁴⁸. Therefore, we will attempt to include all randomized patients, regardless of intervention or length of follow-up in the primary efficacy comparison.

9.2.11.2 mSOFA Scores

mSOFA scores will be assessed as 1) observed cases, 2) LOCF, 3) using MMRM, and 4) categorized and combined with mortality and local activity as part of the primary composite clinical success endpoint, NICCE.

Individually missing mSOFA component values due to non-measurement are conventionally assumed as normal and this convention will be followed for this study.

LOCF will not be applied to missing mSOFA scores after patient death in analyses that employ LOCF to describe mean values of time. Therefore, analysis of SOFA mean values using LOCF will focus on morbidity rather than mortality.

Mixed model repeated measures analyses (MRMM) will utilize implicit imputed values for all missing values including those subsequent to patient death.

In categorical analyses including formulation of the primary efficacy endpoint, an mSOFA value that is greater than 1 at Day 14 is considered a treatment failure in the same fashion as patient death. LOCF for SOFA is necessary to guarantee that every patient has a value at Day 14 for use in determining NICCE among patients that are alive at the Day 28 and who have not otherwise failed due to other NICCE components including more than 3 debridements, or amputation beyond the first debridement.

9.2.11.3 Tipping Point Analysis for Primary Endpoint

If there are any patients with missing primary endpoints, a tipping point sensitivity analysis will be conducted. In this analysis, missing values in each group are separately assumed to be either successes or failures. Treatment group differences are computed based on all possible combinations of assigning success or failure to NICCE to the patients in the 2 groups. For example, one scenario will be that all missing AB103 observations are failures and all missing placebo observations are successes. The next scenario would have one success and the remaining missing values as failure for AB103 and all missing placebo outcomes as successes. For each scenario, the 1-sided p-value for testing the primary effectiveness hypothesis will be determined. These results will be plotted using a dot plot with the number of missings assumed as failures for AB103 on the x-axis and the number of missing assumed as failures for placebo on the Y-axis. The dots will be color coded to indicate whether or not the primary statistical conclusion changes under each individual scenario. If the fraction of scenarios in which the statistical conclusion changes is small, the primary results will have been shown to be robust against assumptions concerning missingness. If there are more than a very small amount of missing data, multiple imputation of missing endpoints may be performed in additional supporting analyses using the SAS procedures, Proc MI and Proc MI Analyze.

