9.1.2 Sample Size Justification

This trial will enroll 290 subjects that will be randomized in a ratio of 1:1 to either AB103 0.50 mg/kg (n=145) or placebo (n=145), each in addition to SoC. Sample size analysis was performed assuming that all patients will be evaluable for the primary endpoint. This assumption is justified since all patients in the Phase 2a trial and in the retrospective study were evaluable for NICCE. The primary efficacy hypothesis will be tested using an unadjusted γ^2 statistic with a 0.01 two-sided significance level. Statistical power was computed for a range of expected treatment group differences supported by the results of preliminary studies. For treatment group differences equal to 0.30, 0.25, and 0.20, statistical power will be equal to 99%, 95.9%, and 80.2%, respectively. These estimates were determined conservatively assuming an average success rate of 0.5. In this way these power estimates are applicable across the range of expected response rates but may be conservative in some cases. The use of NICCE and this range of expected treatment effects is supported by preliminary studies. In the Phase 2a trial, 71.4% (5/7) patients with baseline mSOFA≥3 treated with AB103 0.50 mg/kg achieved NICCE. In contrast, 40% (2/5) placebo patients with baseline mSOFA>3 achieved NICCE, a difference of 0.314. The retrospective study provided further support for the untreated response rate. Among 69 patients with baseline mSOFA≥3, 33.3% (23/69) achieved NICCE, difference of 0.381 relative to Phase 2a treated group. If the observed differences are equal to 0.35, 0.25, and 0.20 (centered about 0.5), then the corresponding 2-sided p-values will be p<0.0001, p<0.0001, and p=0.0007, respectively. The observed difference will need to be larger than about 0.16 (e.g., 0.58 vs 0.42) for p≤0.01. Based on a similar evaluation

of the co-primary endpoint, the study is designed to demonstrate statistical significance at two-sided α =0.05 for co-primary success rates of 0.80 vs 0.60 in the AB103 and placebo groups, respectively. If these are the true success rates, then power will 96.4%. However, if the true rates are 0.78 vs 0.62 (difference = 0.16), then power is 84.8%. The sample size has also been selected to obtain sufficient enrollment on the treatment arm for relevant secondary effectiveness endpoints and for safety endpoints.

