2.1.2 Primary Efficacy Endpoint

To be considered a success in terms of the primary endpoint, each patient must meet all components of NICCE as summarized in the following table.

Component	NICCE
Survival	• Alive at Day 28
Local component	• ≤3 debridements through Day 14
	 No amputation beyond first debridement*
Systemic component	• mSOFA score of ≤1 at Day 14
	 Reduction of ≥3 score points between baseline and Day 14 mSOFA score

^{*}Amputation is defined as removal of a limb or portion of a limb to the level of a joint space

An unadjusted chi-square test using a two-sided type 1 error of α =0.01 will be used to test superiority of Reltecimod relative to placebo for the primary endpoint (NICCE). Primary results will include the numbers and percentages of patients achieving NICCE in each treatment group, the p-value from the chi-square statistic, as well as the estimated treatment group difference in NICCE success rates with 99% confidence interval.

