5.10.2 Handling of Missing Primary Endpoints

As noted above, it is expected to be able to evaluate NICCE in all patients based on the *a priori* specification for this endpoint. If there are any patients with missing primary endpoints, these subjects will be treated as NICCE and CPPE failures in primary analyses and tipping point sensitivity analyses will be conducted. In these analyses, missing values in each group are separately assumed to be either successes or failures. Treatment group differences are computed

based on all possible combinations of assigning success or failure to NICCE to the patients in the two groups. For example, one scenario will be that all missing Reltecimod observations are failures and all missing placebo observations are successes. The next scenario would have one success and the remaining missing values as failure for Reltecimod and all missing placebo outcomes as successes, etc. For each scenario, the hypothetical p-value for testing the primary effectiveness hypothesis will be determined. If there is more than a very few missing values, these results will be plotted using a dot plot with the number of missings assumed as failures for Reltecimod on the x-axis and the number of missing assumed as failures for placebo on the Y-axis. The dots will be color coded to indicate whether or not the primary statistical conclusion changes under each individual scenario. If the fraction of scenarios in which the statistical conclusion changes is small, the primary results will have been shown to be robust against assumptions concerning missingness. If there is more than a small amount of missing data, multiple imputation of missing endpoints may be performed in additional supporting analyses using the SAS procedures, Proc MI and Proc MI Analyze. However, this is not expected to be necessary.

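### The NICCE tipping-point analysis judges robustness by a raw share of scenarios, and patients with a carried-forward Day 14 mSOFA generally stay outside it

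*Protocol*

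**What the plan says.** The primary NICCE test is fixed in SAP 2.1.2: "An unadjusted chi-square test using a two-sided type 1 error of" 0.01. SAP 5.10.2 sets the base case for missing outcomes: "these subjects will be treated as NICCE and CPPE failures in primary analyses and tipping point sensitivity analyses will be conducted".

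The sensitivity analysis varies the number of successes among the missing patients in each arm over all combinations and marks each combination by whether the primary conclusion changes. Both documents end with the same rule: "If the fraction of scenarios in which the statistical conclusion changes is small, the primary results will have been shown to be robust". Neither gives a cut-off or a weighting.

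The documents differ on the p-value. Protocol 9.2.11.3 says: "For each scenario, the 1-sided p-value for testing the primary effectiveness hypothesis will be determined". SAP 5.10.2 rewrites that sentence without any sidedness, and SAP section 1 gives the SAP precedence.

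On the Day 14 score, protocol 9.2.11.2 and SAP 5.10.1 both say: "LOCF for SOFA is necessary to guarantee that every patient has a value at Day 14 for use in determining NICCE". SAP 5.10.2 accordingly expects NICCE to be evaluable in everyone. Multiple imputation is mentioned in both documents as optional, and again only for missing endpoints.

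**The concern.** A tipping-point analysis should show how adverse the unseen outcomes would have to be before the conclusion is lost, so that a reader can judge whether that is believable. A share of equally weighted cells does not do this. It depends on how many patients are missing and how they split between arms, and it gives an implausible cell the same weight as a plausible one.

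The analysis is also aimed at the wrong patients. Two of the five NICCE components depend on the Day 14 mSOFA. A missed Day 14 assessment is foreseeable: protocol 4.3.7 falls back to telephone contact when parameters cannot be collected, and the Day 10 visit (4.3.6) takes place only in hospital. LOCF turns such a patient into a non-missing NICCE, so the grid generally leaves that value alone.

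At stake is what the report may say. The plan authorises in advance a statement that the primary result withstands missing-data assumptions. That statement could be made when the main such assumption, the carried-forward Day 14 score, had not been varied.

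**Working it through.** **Inputs.** 145 per arm (protocol 9.1.2: "This trial will enroll 290 subjects that will be randomized in a ratio of 1:1"). Pooled chi-square, two-sided 0.01, critical z = 2.576 (SAP 2.1.2). Missing counted as failure in the base case (SAP 5.10.2). The documents give no number of missing endpoints and expect none, so every count below is an assumption.

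**Reproducing the plan's figures.** Protocol 9.1.2 states "For treatment group differences equal to 0.30, 0.25, and 0.20, statistical power will be equal to 99%, 95.9%, and 80.2%, respectively", "assuming an average success rate of 0.5". At 0.60 vs 0.40:

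- null SE = √(2×0.25/145) = 0.0587; alternative SE = √(0.48/145) = 0.0575
- power = Φ[(0.20 − 2.576×0.0587)/0.0575] = Φ(0.847) = 80.2%

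The same formula gives 95.9% at 0.25 and 99.6% at 0.30. The p-value at 87 vs 58 is 0.00066, against the stated 0.0007. The test is therefore the one the plan used.

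**Grid.** Let a and b be the numbers of missing AB103 and placebo patients set to success. With m missing per arm there are (m+1)² cells. Cells with a ≥ b number (m+1)(m+2)/2, which is 36 of 64 (56%) at m=7 and 66 of 121 (55%) at m=10. A scan covered all significant results with placebo rates of 0.20–0.60 and AB103 rates up to 0.85, with equal missingness from 3 to 29 per arm. An a ≥ b cell flipped in only 6 to 17 of the 2,205 to 2,618 results, under 1% each time.

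**Example 1: 86 vs 61, 7 missing per arm.**

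| Placebo excess b − a | Example cell | Two-sided p |
|---|---|---|
| 0 | 86 vs 61 | 0.0033 |
| 3 | 86 vs 64 | 0.0097 |
| 4 | 86 vs 65 | 0.0136 |
| 7 | 86 vs 68 | 0.034 |

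The flipped cells are those with b − a ≥ 4: 4+3+2+1 = 10 of 64 (16%). The informative figure is the excess of 4. It can be set against the observed rates, 86/138 = 62% and 61/138 = 44%. These predict about 4.4 and 3.1 successes among 7 missing per arm, an excess of −1.3.

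**Example 2: 87 vs 58.** The tipping excess is 8 (87 vs 66, p=0.0135). With 10 missing per arm, 3+2+1 = 6 of 121 cells (5%) flip, and the worst case (87 vs 68) has p=0.025. With 5, 10, 15 and 20 missing per arm the flipped share is 0%, 5.0%, 14.1% and 20.6%, while the tipping excess stays at 8.

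**Unequal missingness.** For 84 vs 61 with 5 AB103 and 10 placebo patients missing, 39 of 66 cells (59%) flip. Only 21 of 66 cells have a ≥ b.

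**Carried-forward scores.** Reclassify k AB103 successes as failures and leave placebo alone:

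- 87 vs 58: k=7 gives 80 vs 58, p=0.0097; k=8 gives 79 vs 58, p=0.0135.
- 86 vs 61: k=3 gives 83 vs 61, p=0.0098; k=4 gives 82 vs 61, p=0.0136.

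These patients have a NICCE value, so the planned grid contains no cell for them.

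**The case against.** The strongest reply is that this is a supportive analysis with few patients to act on. The plan expects no missing endpoints, and the colour-coded plot already shows the boundary. At the planned 0.20 difference no cell flips with 5 or 7 missing per arm. All of this is correct. However, the SAP draws the plot only when there are more than a very few missing values, and the robustness statement is tied to the share of cells and not to the boundary. A nearly empty grid is also a consequence of LOCF, which is the second part of the concern.

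On Day 14 data, the protocol has mitigations: all efforts to collect, SOFA parameters on the day of discharge, and nurse visits to outpatients from Day 10 (4.3). These should keep the number of carried-forward scores low. They do not test those that remain. The observed-case and MMRM analyses of mSOFA avoid LOCF of total scores but do not re-derive NICCE.

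Three stronger readings are tempting, and the documents do not support them.

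- **Half the grid can never overturn a positive result.** This is nearly true only for about equal missingness with missing counted as failure. With more missing on placebo it fails, as the 39 of 66 example shows.
- **Scenarios will be judged at a one-sided 0.01.** That would cut the flips in Example 1 from 10 to 3 of 64. Neither document states that threshold. The prevailing SAP drops the one-sided wording and refers to the primary conclusion, which is defined at two-sided 0.01. A one-sided p against 0.005 would be equivalent in the favourable direction. A wording mismatch remains.
- **No other missing-data analysis is foreseen.** Multiple imputation is available at discretion, although it has the same restriction to missing endpoints.

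**Conclusion.** The concern holds in two respects, both in the controlling SAP. The robustness rule is an unweighted share with no cut-off, and under about equal missingness it can look reassuring when a modest imbalance would lose significance (16% of cells against an excess of 4 in Example 1). More important, patients with a carried-forward Day 14 mSOFA generally sit outside the only firmly planned sensitivity analysis for missing NICCE data. The word generally is needed, because such a patient who also lacked survival or local-component data could still have a missing NICCE.

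The sizes are illustrations. They assume 145 per arm, the stated success counts and assumed numbers missing. Example 1 starts only three successes above the significance boundary (83 vs 61). The carried-forward examples assume that all errors fall on AB103 successes. At 87 vs 58 the conclusion survives if at least one of the eight is a true success; at 86 vs 61 four errors are enough. How many scores will be carried forward, and in which direction they err, cannot be known from the documents.

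The primary test and its type 1 error are unaffected. What changes is the strength of the robustness claim, so this should be corrected before unblinding.

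**What to change.** In SAP 5.10.2:

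1. Replace the share-of-scenarios rule by the tipping boundary: the smallest excess of placebo over AB103 successes among the missing patients that takes the two-sided chi-square p above 0.01. Judge it against the observed NICCE rates by arm. Always report it, however few patients are missing.
2. For this analysis only, treat as missing every patient whose Day 14 mSOFA was carried forward and who has not failed another component. Say whether this covers component-wise carry-forward (SAP 5.10.1, rule 2) as well as a carried-forward total (rule 3). The boundary may then be a negative excess, and should be reported as such.
3. State that every scenario uses the two-sided 0.01 test, and align the one-sided wording in protocol 9.2.11.3.

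The primary analysis stays as it is. The cost is SAP and protocol wording, a flag for carried-forward scores and a small change to one program. The resulting robustness statement may be less favourable.

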9.2.11.4 Mixed Model Repeated Measures

As describe above, continuous measure observed over time will be assessed using MMRM where possible. MMRM uses all available data and results in implicit imputations for missing data which are valid under MAR, a more general set of assumptions than 'missing completely at random (MCAR)'.

9.3 Safety Analysis

The primary safety measures are AEs (including SAEs), clinical safety laboratory, physical exam, vital signs through Day 28 and ECG (days 0 and 1) and including determination of survival through Day 28.

The safety profiles will be compared between active and placebo groups using descriptive statistics as appropriate for continuous and categorical safety variables. Changes in continuous safety measures such as laboratory values will be summarized by mean changes over time using descriptive statistics (mean, SD, median, minimum and maximum). The presence of clinically significant safety findings will be summarized by shift tables separately for each group using counts and percentages. AEs will be classified according to system organ class and preferred term and summarized by counts and percentages separately for those recorded on Day 0 (prior to drug administration) and those with onset on Day 1 or later. AEs will also be summarized by relationship to study drug, severity, and whether they are serious. Specific summaries will involve AEs and SAEs in the Infection/Infestation system organ class (SOC). Electrocardiogram results from Day 0 and Day 1, and change from Day 0 to Day 1 will be summarized using mean, median, standard deviation, minimum, and maximum values. Results from physical exams will be tabulated

for the Day 0, Day 7, and Day 14. For each test, the number of patients evaluated, and the numbers and percentages of patients with Normal and Abnormal results will be tabulated. Vital signs including weight, temperature, systolic BP, diastolic BP, respiration rate, and heart rate will be summarized across time (Day 0, Day 1, Day 2, Day 3, Day 7, and Day 14 separately by treatment group by N, Mean, and SD.

